11.2.2. Subject Populations for Analysis

A subject will be defined as screened after the signature of the informed consent, regardless of the completion of all the screening procedures.

A subject will be defined as eligible if he/she meets all the inclusion/exclusion criteria. Otherwise he/she will be defined as a screen failure.

A subject will be defined as enrolled in the study if he/she is included into the evaluation phase of the study.

An eligible but not enrolled subject will be defined as a reserve.

The following analysis populations will be defined for this study:

Per protocol: will include any subject randomized into the study that receives a dose of study drug and that has completed at least one post-baseline efficacy measurement while on study medication;

Safety: Any subject randomized into the study that receives a dose of study drug;

Intent to Treat: Any subject who is randomized and receives the protocol required study drug exposure and required protocol processing.

Efficacy analyses will be performed on the Intent-to-Treat population and the Per-Protocol population. Safety summaries will be based on Safety set. Subject characteristics will be presented for all subjects randomized.

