- 6. Females of child-bearing potential (not surgically sterile or post-menopausal, defined as 12 months without menses) will use an acceptable method of contraception from 1 month prior to randomization (or screening, if earlier) through 1 month following the last dose of study medication. Examples of acceptable methods of contraception for females include abstinence, double barrier method, IUD, hormonal contraception, or sterilized partner;
- 7. Ability and acceptance to provide written informed consent;
- 8. Willing to participate in the pharmacogenomics sample collection;
- 9. Willing and able to comply with all study requirements and restrictions
- 10. Willing to not participate in any other interventional trial for the duration of their participation.

Exclusion Criteria:

- 11. Unable or unwilling to provide informed consent or to comply with study procedures.
- 12. Unwilling to agree to provide pharmacogenomics sample
- 13. Diagnosis of gastrointestinal diseases.
- 14. Structural or metabolic diseases that affect the GI system.

- 15. Unable to avoid the following over-the-counter medications 48 hours prior to the receipt of study medication and throughout the study:
- 16. Medications that alter GI transit including laxatives, magnesium and aluminum containing antacids, prokinetics, erythromycin;
- 17. Analgesic drugs including NSAIDs and COX-2 inhibitors

NOTE: Stable doses of thyroid replacement, estrogen replacement, low-dose aspirin for cardioprotection, and birth control are permissible.

- 18. History of recent surgery (within 60 days of screening).
- 19. Pregnant or nursing;
- 20. History of intolerance and/or hypersensitivity to medications similar to tradipitant and its accompanying excipients;
- 21. History (including family history) or current evidence of congenital long QT syndrome or known acquired QT interval prolongation (including QTcF > 450 in males or > 470 in females at screening);
- 22. History of suicide attempt and/or suicidal ideation (of type 4 or 5 on the Columbia Suicide Severity Rating Scale (C-SSRS)) within 2 years of screening or subject is at risk of suicide at Screening or Baseline visits, in the opinion of the investigator;
- 23. Recent history (within six months of screening) of Alcohol Use Disorder or Substance Use Disorder which may include a positive drug screen at the Screening visit;

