11.2.1. General

Statistical analyses will be performed using two-sided tests.

Data will be summarized by treatment group (and by visit when applicable), with respect to demographic and baseline characteristics, efficacy variables, and safety variables.

Summary statistics will include the mean, N, standard deviation, median, minimum, and maximum values for continuous variables, and frequencies and percentages for categorical variables.

Continuous efficacy variables will be analyzed using a mixed-effect model for repeated measures (MMRM) and/or an analysis of covariance (ANCOVA) model. The models will be described in the SAP.

For the analyses of change from baseline, only subjects with a baseline and at least one (1) post-baseline measure (GE, NDT, GA) will be included in the per protocol analysis. Unless otherwise

specified, baseline is defined as the latest non-missing observation across all the visits in the screening phase, before the active study drug begins. Endpoint will be the latest non-missing observation across all the post-baseline visits in the evaluation phase. A per protocol analysis of efficacy will be conducted using data actually collected and without any imputed data .

Categorical variables will be analyzed using the Cochran-Mantel-Haenszel (CMH) test blocking on sites, and Fisher's exact test will be used when site is not adjusted (mainly for safety assessment).

Details of the model and the analyses will be specified in the SAP. All statistical analyses will be performed using SAS®, Version 9.1.3 or higher.

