11.2.5. Study Medication

The number of subjects at each visit will be summarized by treatment group.

The compliance to study medication, as recorded in the CRF, will also be summarized by treatment group. The proportion of subjects who are significantly noncompliant in the double-blind phase will be summarized by treatment groups.

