11.2.6. Prior/Concomitant Therapy

Any medications or therapy present before the first dose of study medication (Visit 2) will be considered as prior medications. Concomitant medications (medications present while on study medication) will be recorded throughout the study and at early discontinuation. These medications will be coded using the WHO-drug dictionary. The number of subjects from the Safety Population using prior or concomitant medications will be categorized by the WHO-drug category and preferred term, and presented for each treatment group. In any given category (e.g., drug category) a subject will be counted only once.

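### The set named Per protocol has no adherence, prohibited-drug or test-validity rule, and the only exposure condition sits under Intent to Treat; the two labels look interchanged

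*SAP*

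**What the plan says.** SAP 11.2.2 defines two efficacy sets and analyses efficacy on both, without naming either as the main one.

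- Per protocol takes randomized subjects under the condition "that receives a dose of study drug and that has completed at least one post-baseline efficacy measurement while on study medication".
- Intent to Treat is "Any subject who is randomized and receives the protocol required study drug exposure and required protocol processing".

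SAP 11.2.1 adds three rules. For change-from-baseline analyses, "only subjects with a baseline and at least one (1) post-baseline measure (GE, NDT, GA) will be included in the per protocol analysis". On missing data, "A per protocol analysis of efficacy will be conducted using data actually collected and without any imputed data". On the value to analyse, "Endpoint will be the latest non-missing observation across all the post-baseline visits in the evaluation phase".

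The information that could identify departures from protocol is collected but only reported. On dosing, 11.2.5 says "The proportion of subjects who are significantly noncompliant in the double-blind phase will be summarized by treatment groups". On other drugs, 11.2.6 says "Concomitant medications (medications present while on study medication) will be recorded throughout the study and at early discontinuation", followed by coding and tabulation.

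The protocol synopsis excludes at entry anyone "Unable to avoid the following over-the-counter medications 48 hours prior to the receipt of study medication and throughout the study". The list under it includes laxatives, certain antacids, prokinetics and erythromycin. No consequence for the analysis is given if a subject later breaks the restriction.

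The synopsis (Overall Design) also says that subjects who withdraw consent after randomization stay in an intent-to-treat analysis with imputed data. Subjects who start medication but do not finish testing through Day 9 are replaced. Missed doses are not mentioned.

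**The concern.** A per-protocol analysis is meant to show the effect in subjects who took the drug as planned and were tested validly. Under 11.2.2, one dose and one on-treatment measurement are enough. A subject who missed most doses before the SPECT day, or who took a prokinetic before scintigraphy, is a per-protocol subject, and the latest non-missing result is the endpoint. In effect the set is a modified intent-to-treat set under another name.

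The set called Intent to Treat carries the restriction that a reader would expect of Per protocol. A reader of the study report would therefore take the looser set for the adherent one and the restricted set for the randomized comparison. With 12 subjects per group and gastric emptying among the primary endpoints, one or two such subjects can change what each analysis shows.

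**Working it through.** **Comparing the definitions**

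| Condition | Per protocol (11.2.2) | Intent to Treat (11.2.2) | Intent to treat (synopsis) |
|---|---|---|---|
| Randomized | yes | yes | yes |
| Dosing | one dose | the required exposure | none stated |
| Testing | one post-baseline measurement on medication | the required processing | none; missing data imputed |
| Noncompliance (11.2.5) | not used | not named | not used |
| Prohibited drugs | not used | not named | not used |
| Withdrawal of consent after randomization | kept if one measurement was made | out if exposure or processing is incomplete | kept |

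The Intent to Treat column is the restrictive one, and it disagrees with the synopsis in the last row. The on-medication phrase in Per protocol is not defined and has to hold for one measurement only. In 11.2.6 the same phrase appears to mean the treatment period. It is a timing condition, not an adherence threshold.

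**Reproducing the plan's figures**

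Inputs from SAP 11.1 and Table 7: n = 12 per group, 80% power, α = 0.05, unpaired t-test; two-sided per 11.2.1. Accommodation: mean 507 mL, SD 100, detectable difference 119.7 mL. T1/2: mean 122 min, SD 29.8, detectable difference 35.6 min.

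The noncentrality is δ / (SD × √(1/n₁ + 1/n₂)), and power comes from the noncentral t with n₁ + n₂ − 2 degrees of freedom.

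- Accommodation: 119.7 / (100 × √(2/12)) = 119.7 / 40.82 = 2.932. With 22 df and critical value 2.074, power is 80.0%. 119.7/507 = 23.6%.
- T1/2: 35.6 / (29.8 × √(2/12)) = 35.6 / 12.17 = 2.926. Power is 79.9%. 35.6/122 = 29.2%.

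Both match the plan. The sample-size figures are not in question.

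**Illustration of size**

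Assumption: k of 12 tradipitant subjects show no drug effect, with k from 0 to 3. The documents give no rate, so this range is mine. If these subjects are kept, the expected difference is 119.7 × (1 − k/12). If they are excluded, the difference stays at 119.7 mL and the groups are 12 and 12 − k.

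| k | Difference if kept (mL) | Power if kept, SD 100 | Power if kept, with mixture variance | Power if excluded |
|---|---|---|---|---|
| 0 | 119.7 | 80% | 80% | 80% |
| 1 | 109.7 | 73% | 71% | 78% |
| 2 | 99.8 | 65% | 61% | 76% |
| 3 | 89.8 | 56% | 51% | 73% |

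The mixture column adds f(1 − f) × 119.7², with f = k/12, to the tradipitant variance and averages the two group variances. For k = 2 the pooled SD is 104.9.

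For T1/2 the differences if kept are 35.6, 32.6, 29.7 and 26.7 min. Power at constant SD is 80%, 73%, 64% and 56% if kept, and 80%, 78%, 76% and 73% if excluded.

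At constant SD, exclusion therefore gains about 5, 11 and 17 percentage points for k = 1, 2 and 3. It does not return power to 80%. The exclusion column also assumes that the excluded subjects do not differ from the rest in their underlying gastric function.

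**The case against.** The strongest reply is that an analysis restricted by exposure and processing is already planned: it is the one called Intent to Treat. That is correct. A reader might infer from the Per protocol wording that the plan has no analysis of adequately dosed and tested subjects, and the documents do not support that. What stands is that this analysis has the wrong name, that its required exposure and processing are not spelled out in 11.2.2, and that it contradicts the synopsis.

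It also follows that tightening Per protocol alone would do harm. Both efficacy sets in 11.2.2 would then be restricted, and no all-randomized efficacy set would remain there. At present only subject characteristics are presented for all randomized subjects.

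Four further points are fair.

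- It would be too strong to say that the Per protocol set excludes nobody. Subjects never dosed, or with no on-medication measurement, are out. They are not out for poor adherence or a prohibited drug.
- A reader might take the 48 hours in the synopsis as a window before each test. The text sets it before receipt of study medication and then continues the restriction throughout the study.
- The text available does not define significant noncompliance, and it does not contain the test meal and drink specifications. A rule built on them needs a threshold or a cross-reference.
- SAP 11.2.1 defers details of the model and analyses to a further SAP that is not among the documents. It might add criteria. However, 11.2.2 states the populations outright and does not defer them.

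Finally, this is a Phase I study in healthy volunteers, and compliance and concomitant drugs will be reported by group. That limits the consequences but does not correct the definitions.

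**Conclusion.** The point holds as a fault in the definitions. As written, Per protocol is a modified intent-to-treat set, Intent to Treat is the restricted set, and the latter conflicts with the synopsis. This rests on the text alone and on no assumption about adherence.

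The power figures are illustrative. They assume 1 to 3 of 12 tradipitant subjects with no effect and, in the main comparison, an unchanged SD. They do not quantify the effect of a prohibited drug, whose direction and size the documents do not give. A reader might infer that the trial will lose 7 to 24 points of power because of this wording. The documents do not support that: they give no non-adherence rate, and exclusion would recover only part of the loss. An all-randomized analysis would also carry the dilution, and properly so.

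The definitions should be corrected before unblinding. Doing so needs no change to the design or sample size.

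**What to change.** Before unblinding:

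1. In 11.2.2, define Intent to Treat as all randomized subjects, consistent with the synopsis (Overall Design), and name it the main efficacy set. Say that subjects who are replaced remain in it.
2. Move the required-exposure and required-processing condition to Per protocol and spell it out. On blinded review, exclude subjects or individual tests for any of three reasons:
   - significant noncompliance under 11.2.5, with the threshold stated or cross-referenced;
   - breach of the synopsis medication restriction as it is written, that is, from 48 hours before study medication and throughout the study;
   - a SPECT, scintigraphy or satiation test not done as the protocol specifies.
3. Align 11.2.1: use the same Per protocol definition there, and in that analysis take the latest valid observation as the endpoint, not merely the latest non-missing one.

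The cost is SAP wording and one blinded review of compliance, concomitant-medication and test records. Compliance and concomitant drugs are already recorded. The drawback is that the per-protocol set may lose a few of 24 subjects. Because it is selected after randomization, it can be biased and should remain supportive of the all-randomized analysis.

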11.2.3. Subject Disposition

Study completion and reasons for discontinuation for all randomized subjects in the double-blind phase will be summarized for each treatment group. Discontinuations by reason will be tabulated by visit for each treatment group.

11.2.4. Demography and Other Baseline Data

Demographic data and subject characteristics at screening/baseline will be listed and summarized by treatment group for all randomized subjects using descriptive statistics.

Past and current medical history will be summarized by treatment group using the system organ class (SOC) as coded using the Medical Dictionary for Regulatory Activities (MedDRA) coding dictionary.

Past medical conditions will be defined as an onset date prior to enrolling (Visit 1) and resolved (not on-going) as of Visit 1. Current medical conditions, defined as an onset date on or after the date of enrolling (Visit 1) or an onset date prior to enrolling (Visit 1) and unresolved (on-going) as of Visit 1, will be reported separately, but similarly to the past medical conditions. If both a past and a current (on-going) medical condition record are indicated for a condition, the condition will be presented under current medical conditions only.

11.2.5. Study Medication

The number of subjects at each visit will be summarized by treatment group.

The compliance to study medication, as recorded in the CRF, will also be summarized by treatment group. The proportion of subjects who are significantly noncompliant in the double-blind phase will be summarized by treatment groups.

11.2.6. Prior/Concomitant Therapy

Any medications or therapy present before the first dose of study medication (Visit 2) will be considered as prior medications. Concomitant medications (medications present while on study medication) will be recorded throughout the study and at early discontinuation. These medications will be coded using the WHO-drug dictionary. The number of subjects from the Safety Population using prior or concomitant medications will be categorized by the WHO-drug category and preferred term, and presented for each treatment group. In any given category (e.g., drug category) a subject will be counted only once.

11.3. Efficacy Data Analysis

11.3.1. Primary Outcome and Methodology

The primary objectives of this study are:

• Comparison of fasting gastric volume induced by tradipitant vs. placebo studied by single photon emission computed tomography (SPECT)

- Comparison of accommodation volume induced by tradipitant vs. placebo studied by SPECT
- Comparison of volume to fullness (VTF, mL) on satiation test for tradipitant vs. placebo
- Comparison of gastric emptying T_{1/2} of solids on scintigraphy for tradipitant vs. placebo
- Comparison of gastric emptying at 2 and 4 hours

11.3.2. Secondary Efficacy Analysis

The secondary efficacy outcomes include:

- Absolute postprandial gastric volume
- Gastric volume (GV) ratio (postprandial/fasting GV)
- Gastric emptying of solids at 2h
- Gastric emptying of solids at 4h
- Intragastric meal distribution at time zero, (IMD⁰) following ingestion of test meal
- Maximum tolerated volume (MTV) during satiation test
- Aggregate symptoms score 30 min after MTV on satiation test
- Individual symptom scores (nausea, bloating, fullness, pain) on satiation test

Continuous endpoints will be summarized and analyzed in a manner similar to the primary endpoint. Details of the analysis will be described in the SAP.

Categorical variables will be evaluated as described in the SAP. Time to event data will be analyzed using the Kaplan-Meier method, and the treatment group differences will be tested by the log-rank test. Details of the analysis will be described in the SAP.

11.4. Safety Data Analysis

The primary assessment of safety will be based on the frequency of treatment-emergent adverse events (TEAEs), serious adverse events (SAEs) and on the frequency of clinically notable abnormal vital signs, electrocardiograms (ECGs) and laboratory values. Other safety evaluations include changes in vital signs, changes in clinical laboratory evaluations, and changes in ECGs, physical exam findings during treatment, and suicide ideation and behavior events.

11.4.1. Adverse Events

Adverse events will be recorded throughout the study and at early discontinuation. Adverse events and medical conditions will be coded using the Medical Dictionary for Regulatory Activities (MedDRA) coding dictionary. Treatment-emergent adverse events will be defined as those events,

which are newly occurring or worsening from baseline. In all cases only treatment emergent adverse events will be summarized.

Treatment-emergent adverse events will be summarized within each treatment group by primary system organ class (SOC) and preferred term. (*NOTE*: In any given category [e.g. body system] a subject will only be counted once.) The incidence rates of TEAEs will be analyzed as described in the SAP. Similar displays will be provided for SAE and prior (conditions ending prior to the first dose of study medication and current (conditions present while on study medication) medical conditions.

Adverse events will further be categorized by severity, relationship to study medication, and action taken. Other information collected will be listed, as appropriate. Any event starting more than 3 days after the final dose of study medication will be excluded from the above tables and only listed, unless the event caused discontinuation.

The proportions of subjects experiencing SAEs and AEs resulting in discontinuation from the study will be summarized by treatment groups.

11.4.2. Laboratory Data

Clinical Laboratory Data

The summary statistics of raw data (hematology and chemistry) and change from baseline values will be presented, as well as shift tables from baseline to post-baseline values using normal ranges. For urinalysis parameters, the number and percentage of subjects falling under each category of the test will be presented.

Clinical laboratory data will be summarized for each treatment group by presenting the proportions of subjects with clinically notable abnormalities (Appendix 18).

Clinically notable values will be identified according to the criteria identified in the FDA's "Supplementary Suggestions for Preparing an Integrated Summary of Safety Information in an Original NDA Submission and for Organizing Information in Periodic Safety Updates" (Revised 2-APR-87) provided by the FDA Division of Neuropharmacological Drug Products (DNDP). Differences in incidence rates between the treatment groups will be tested as described in the SAP.

11.4.3. Vital Signs and Body Measurements

Data from vital signs and body measurements will be listed, clinically notable values (Appendix 20.2) will be flagged, and any other information collected will be listed. Data will also be summarized by treatment group using mean change from baseline and proportions of subjects with values outside the normal range, and values that were clinically notable.

11.4.4. Electrocardiogram (ECG)

Results from the ECG will be listed for each subject. These data will also be summarized for each treatment group by presenting subjects with newly occurring or worsening ECG abnormalities.

11.4.5. C-SSRS

Results from the C-SSRS will be listed for each subject. These data will also be summarized by treatment group and for suicidal ideation events, suicidal behaviors and completed suicides. In particular, for each of the following suicide related events, the number and percent of subjects with the event will be enumerated by treatment group: completed suicide, nonfatal suicide attempt, interrupted attempt, aborted attempt, preparatory acts or behavior, active suicidal ideation with specific plan and intent, active suicidal ideation with some intent to act without specific plan, active suicidal ideation with any methods (no plan) without intent to act, non-specific active suicidal thoughts, and wish to be dead. Details of the analysis will be provided in the SAP.

